1.1.2 Secondary Objectives

Clinical Objectives

- To assess and characterize associations between inflammatory pustular dermatoses and systemic manifestations from ophthalmologic, cardiovascular, gastrointestinal, rheumatologic and immunologic perspectives.
- To assess the changes in quality of life and functional measures during the course of anakinra therapy.
- To determine adequate dosing and safety and assess toxicity with the use of anakinra in the management of inflammatory pustular dermatoses.

Laboratory Objectives

- To characterize and analyze inflammatory pathways in skin and peripheral blood mononuclear cells using immunohistochemistry, cytokine and gene expression studies.
- To evaluate systemic inflammation in patients with pustular dermatoses using novel imaging modalities, and assess biomarkers of cardiometabolic disease using novel techniques including nuclear magnetic resonance spectroscopy (NMR) and HDL cholesterol efflux capacity.
- To evaluate keratinocyte responses to targeted inflammatory stimuli including infectious agents and danger molecules.

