3.4 QUALITY OF LIFE TOOLS/QUESTIONNAIRES

The following quality of life instruments will be administered at baseline, week 4, week 8 and week 12:

1. 36-item Short Form Health Survey is a self-administered multi-purpose, short-form health survey with 36 questions yielding an 8-scale profile of functional health and well-being scores as well as psychometrically-based physical and mental health summary measures and a preference-based health utility index. It is a generic measure. This scale has been used for the measurement of general health status quality of life. This questionnaire will be administered at baseline, week 4, week 8, week 12 and week 16. (10-12 minutes) (**APPENDIX E: SHORT FORM 36 (ENGLISH AND SPANISH)**)
2. Dermatology Life Quality Instrument (DLQI) is a 10-item questionnaire which assesses impact of skin disease on life quality. It is a validated questionnaire which has been used in 33 different skin conditions in 32 countries and is available in 55 languages. It is the most frequently used instrument in studies of randomized controlled trials in dermatology. This questionnaire will be administered at baseline, week 4, week 8, week 12 and week 16. (2 minutes) (**APPENDIX F: DERMATOLOGY LIFE QUALITY (ENGLISH AND SPANISH)**)

Abbreviated Title: Anakinra in pustular dermatoses

Version Date: December 12, 2018

[figure not shown]
3. Pruritus Visual Analog Scale is a self-administered psychometric response instrument which measures subjective characteristics or attitudes that cannot be directly measured. It ranges from 0-10. This scale has been used for measurement in a variety of dermatologic settings. This questionnaire will be administered at baseline, week 4, week 8, week 12 and week 16. (1 minute) (**APPENDIX H: PUSTULAR DERMATOSIS CLINICAL ASSESSMENT SCALE**)
4. Skin Pain Visual Analog Scale is a self-administered psychometric response instrument which measures subjective characteristics or attitudes that cannot be directly measured. It ranges from 0-10. This scale has been used for measurement in a variety of dermatologic settings. This questionnaire will be administered at baseline, week 4, week 8, week 12 and week 16. (1 minute) (**APPENDIX H: PUSTULAR DERMATOSIS CLINICAL ASSESSMENT SCALE**)

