• Bathing or dressing yourself	 ₁	 ₂	 ₃

Abbreviated Title: Anakinra in pustular dermatoses

Version Date: December 12, 2018

4. During the past 4 weeks, how much of the time have you had any of the following problems with your work or other regular daily activities as a result of your physical health?

	All of the time	Most of the time	Some of the time	A little of the time	None of the time
	▼	▼	▼	▼	▼
a. Cut down on the amount of time you spent on work or other activities					
b. Accomplished less than you would like					
c. Were limited in the kind of work or other activities					
d. Had difficulty performing the work or other activities (for example, it took extra effort)					

5. During the past 4 weeks, how much of the time have you had any of the following problems with your work or other regular daily activities as a result of any emotional problems (such as feeling depressed or anxious)?

	All of the time	Most of the time	Some of the time	A little of the time	None of the time
	▼	▼	▼	▼	▼
a. Cut down on the amount of time you spent on work or other activities					
b. Accomplished less than you would like					
c. Did work or other activities less carefully than usual					

Abbreviated Title: Anakinra in pustular dermatoses

Version Date: December 12, 2018

6. During the past 4 weeks, to what extent has your physical health or emotional problems interfered with your normal social activities with family, friends, neighbors, or groups?

Not at all	Slightly	Moderately	Quite a bit	Extremely
▼	▼	▼	▼	▼

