10. Durante las últimas 4 semanas, ¿cuánto tiempo su salud física o sus problemas emocionales han dificultado sus actividades sociales (como visitar amigos, parientes, etc.)?

Siempre	Casi siempre	Algunas veces	Casi nunca	Nunca
▼	▼	▼	▼	▼
 1	 2	 3	 4	 5

Abbreviated Title: Anakinra in pustular dermatoses

Version Date: December 12, 2018

11. ¿Qué tan CIERTA o FALSA es cada una de las siguientes frases para usted?

	Claramente cierta	Mayormente cierta	No sé	Mayormente falsa	Claramente falsa
a	▼	▼	▼	▼	▼
Parece que yo me enfermo un poco más fácilmente que otra gente.....	 1	 2	 3	 4	 5
b					
Tengo tan buena salud como cualquiera que conozco	 1	 2	 3	 4	 5
c					
Creo que mi salud va a empeorar	 1	 2	 3	 4	 5
d					
Mi salud es excelente.....	 1	 2	 3	 4	 5

¡Gracias por contestar estas preguntas!

SF-36v2™ Health Survey © 1992, 2002 Health Assessment Lab, Medical Outcomes Trust and QualityMetric Incorporated. All rights reserved.
SF-36® is a registered trademark of Medical Outcomes Trust.
(IQOLA SF-36v2 Standard, United States (Spanish))

La recopilación de esta información está autorizada bajo el Código de los Estados Unidos, número 42 USC 285. La información que usted proporcione será usada principalmente para evaluar su salud y calidad de vida. Esta información podría ser compartida con doctores e investigadores para fines de investigación o con monitores para garantizar que se mantengan las normas de seguridad. El proveer esta información es voluntario.

Abbreviated Title: Anakinra in pustular dermatoses

Version Date: December 12, 2018

How to Score the Rand SF-36 Questionnaire		
Step 1: Scoring Questions:		
QUESTION NUMBER	ORIGINAL RESPONSE	RECORDED VALUE
1, 2, 20, 22, 34, 36	1	100
	2	75
	3	50
	4	25
	5	0
3, 4, 5, 6, 7, 8, 9, 10, 11, 12	1	0
	2	50
	3	100
13, 14, 15, 16, 17, 18, 19	1	0
	2	100
21, 23, 26, 27, 30	1	100
	2	80
	3	60
	4	40
	5	20
	6	0

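### The SF-36 scoring key in Appendix E does not fit the form administered, so four of the eight scales are wrongly scored or cannot be scored as written

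*Combined protocol and SAP*

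**What the plan says.** Section 1.1.2 lists as a secondary clinical objective "To assess the changes in quality of life and functional measures during the course of anakinra therapy". Section 3.4 describes the SF-36 as a "short-form health survey with 36 questions yielding an 8-scale profile of functional health and well-being scores" and points to Appendix E. The item text in section 3.4 and the calendar in section 3.6 place it at baseline and weeks 4, 8, 12 and 16.

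Appendix E contains two things:

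- **The form, in English and Spanish.** Question 4 asks "how much of the time have you had any of the following problems with your work or other regular daily activities" because of physical health, and question 5 asks the same about emotional problems. Questions 4, 5 and 9 all carry the options "All of the time Most of the time Some of the time A little of the time None of the time". The Spanish form has the same five options with boxes numbered 1 to 5, and its footer identifies it as "SF-36v2™ Health Survey © 1992, 2002 Health Assessment Lab" and "IQOLA SF-36v2 Standard, United States (Spanish".
- **A scoring sheet**, "How to Score the Rand SF-36 Questionnaire". Its first step treats items "13, 14, 15, 16, 17, 18, 19" as two-level (1 scores 0, 2 scores 100). It treats items 23, 26, 27 and 30 as six-level running down from 100 to 0 in steps of 20, and items 24, 25, 28, 29 and 31 as six-level running up from 0 to 100. It also states that every question is scored from 0 to 100.

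Neither section 3.4 nor section 8 gives any other SF-36 scoring rule.

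**The concern.** The form and the key disagree on how many answers the role, energy and emotional well-being items have. An analyst following the key would find no value for three of the five possible answers on the role items. A patient limited most of the time would receive the best possible score there. For energy and emotional well-being the scores exist but are compressed.

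This is an open-label, single-arm study with 25 evaluable patients, so the SF-36 result is the within-patient change. If all of a patient's answers on a role scale move from *Most of the time* to *None of the time*, a clear improvement, the key takes that scale from 100 to no score at all. Leaving the analyst to invent a recode after seeing the data would put an unplanned choice into a stated secondary objective.

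**Working it through.** **Item numbering.** The key numbers items 1-36 and the form numbers questions 1-11, with no crosswalk printed. Counting in order gives Q1=1, Q2=2, Q3a-j=3-12, Q4a-d=13-16, Q5a-c=17-19, Q6=20, Q7=21, Q8=22, Q9a-i=23-31, Q10=32, Q11a-d=33-36. The scale names in the sheet's second step agree with this mapping.

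**The sheet's own example.** Answers of 4 on item 23, 3 on item 27 and 3 on item 29, with item 31 blank, give (40 + 60 + 40)/3 = 46.7, as printed. The key has therefore been read correctly.

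**Options on the form against levels in the key.**

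| Items | Scale | Options on form | Levels in key |
|---|---|---|---|
| 13-16 | Role-physical | 5 | 2 |
| 17-19 | Role-emotional | 5 | 2 |
| 23, 27, 29, 31 | Energy/fatigue | 5 | 6 |
| 24, 25, 26, 28, 30 | Emotional well-being | 5 | 6 |
| The other 20 items | Physical functioning, social functioning, pain, general health, and item 2 (in no scale) | 3, 5 or 6 | Same as form |

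Mismatched items: 4 + 3 + 4 + 5 = 16 of 36. They are all the items of four scales, and no item of the other four.

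**Role scales.** Option 1 scores 0, option 2 scores 100, and options 3, 4 and 5 have no value. The sheet's example averages only the items that have a score. If options 3-5 are dropped in that way on role-physical:

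- Answers 1, 5, 5, 5 (one severe limitation, otherwise none) score 0.
- Answers 2, 2, 2, 2 (limited most of the time on every item) score 100.

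With even five-level coding (1=0, 2=25, 3=50, 4=75, 5=100) the same patients score (0 + 100 + 100 + 100)/4 = 75 and (25 + 25 + 25 + 25)/4 = 25. The printed key reverses their order.

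**Energy/fatigue.** Items 23 and 27 are positively worded; 29 and 31 are negatively worded.

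- Best attainable: (100 + 100 + 80 + 80)/4 = 90.
- Worst attainable: (20 + 20 + 0 + 0)/4 = 10.

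**Emotional well-being.** Items 26 and 30 are positively worded; 24, 25 and 28 are negatively worded. Terms are in the order 24, 25, 26, 28, 30.

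- Best attainable: (80 + 80 + 100 + 80 + 100)/5 = 88.
- Worst attainable: (0 + 0 + 20 + 0 + 20)/5 = 8.
- All middle answers: (40 + 40 + 60 + 40 + 60)/5 = 48.

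Both scales span 80 points (90 - 10 and 88 - 8) instead of 100. A one-option step on an item moves it 20 points where an even five-level scale gives 25, and 20/25 = 80%.

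**Effect of the recode.** With even five-level spacing, the answers in the sheet's example give (25 + 50 + 50)/3 = 41.7 instead of 46.7, and all eight scales can reach 0 and 100.

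**The case against.** The mismatch itself cannot be disputed. It is not a conversion fault: five options appear in both languages, and the Spanish boxes are numbered. The objections concern reach, remedy and weight.

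- **The sheet may be a generic handout.** Section 3.4 cites Appendix E as the instrument, not as a scoring rule, and section 8 is silent. It also names summary measures and a utility index that the sheet does not score, so other software may be intended. None is specified, and this is the only SF-36 scoring instruction in the documents. If something else is used, the sheet still has to go.
- **The answers are not lost.** This stands. Completed questionnaires are kept until analysis is finished. It is the printed key that fails, and a fitting key would recover the scores.
- **The 80% factor is exact only for complete forms.** This stands. With middle answers throughout, energy scores (60 + 60 + 40 + 40)/4 = 50, but (60 + 60 + 40)/3 = 53.3 if item 31 is blank, an apparent change where none occurred. With complete data the factor is constant, so direction and ranking of changes on these two scales survive. That does not help the role scales.
- **The recode is an assumption.** This stands as a caveat: the documents contain no SF-36v2 key. The proposed spacing is the one the sheet already uses for its own five-option items.
- **The weight is modest.** The primary TBSAI50 endpoint is untouched, no sample size or test rests on the SF-36, and the DLQI, the visual analogue scales and the HAQ also cover symptoms, function or quality of life. That argues against treating it as critical, but a stated rule that gives wrong scores for a stated objective should still be corrected.

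**Conclusion.** The concern holds. The key as printed is wrong for the form as printed on 16 of 36 items and 4 of 8 scales. Role-physical and role-emotional have no value for three of five answers and give a near-worst answer the top score. On complete forms energy/fatigue is confined to 10-90 and emotional well-being to 8-88, which contradicts the sheet's own 0-100 statement and shrinks changes to 80% of those under even five-level coding.

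This rests on numbering the form's items in order, which the scale names support, and on treating the English form as the same version as the Spanish one. The version label is printed only on the Spanish form, but the five-option layout is identical. The consequence is limited to a secondary measure and can be reversed from the retained answers. It should be corrected before the SF-36 is analysed.

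**What to change.** Replace the levels for the mismatched items in the Appendix E scoring table:

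- Items 13-19, 24, 25, 28, 29 and 31: 1=0, 2=25, 3=50, 4=75, 5=100.
- Items 23, 26, 27 and 30: 1=100, 2=75, 3=50, 4=25, 5=0.

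Leave the other 20 items unchanged; their option counts already match. Item 21 has six options on the form and keeps its six levels. The sponsor should confirm the recode against the scoring instructions for the version administered, and print the crosswalk from questions 1-11 to items 1-36. If the summary measures and utility index named in section 3.4 are to be reported, their scoring needs to be stated as well. Any forms already scored with the current sheet should be re-scored.

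The cost is one replaced table and a rerun of the scoring from retained answers, with no new data and no burden on patients.

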18 APPENDIX F: DERMATOLOGY LIFE QUALITY (ENGLISH AND SPANISH)

DERMATOLOGY LIFE QUALITY INDEX

DLQI

Hospital No:

Date:

Name:

Score:

Address:

Diagnosis:

The aim of this questionnaire is to measure how much your skin problem has affected your life OVER THE LAST WEEK. Please tick ✓ one box for each question.

- | | | | |
|------------|---|--|---------------------------------------|
| 1. | Over the last week, how itchy, sore, painful or stinging has your skin been? | Very much 
A lot 
A little 
Not at all  | |
| 2. | Over the last week, how embarrassed or self conscious have you been because of your skin? | Very much 
A lot 
A little 
Not at all  | |
| 3. | Over the last week, how much has your skin interfered with you going shopping or looking after your home or garden ? | Very much 
A lot 
A little 
Not at all  | Not relevant  |
| 4. | Over the last week, how much has your skin influenced the clothes you wear? | Very much 
A lot 
A little 
Not at all  | Not relevant  |
| 5. | Over the last week, how much has your skin affected any social or leisure activities? | Very much 
A lot 
A little 
Not at all  | Not relevant  |
| 6. | Over the last week, how much has your skin made it difficult for you to do any sport ? | Very much 
A lot 
A little 
Not at all  | Not relevant  |
| 7. | Over the last week, has your skin prevented you from working or studying ? | Yes 
No  | Not relevant  |
| | If "No", over the last week how much has your skin been a problem at work or studying ? | A lot 
A little 
Not at all  | |
| 8. | Over the last week, how much has your skin created problems with your partner or any of your close friends or relatives ? | Very much 
A lot 
A little 
Not at all  | Not relevant  |
| 9. | Over the last week, how much has your skin caused any sexual difficulties ? | Very much 
A lot 
A little 
Not at all  | Not relevant  |
| 10. | Over the last week, how much of a problem has the treatment for your skin been, for example by making your home messy, or by taking up time? | Very much 
A lot 
A little 
Not at all  | Not relevant  |

Please check you have answered EVERY question. Thank you.

©AY Finlay, GK Khan, April 1992. This must not be copied without the permission of the authors.

Collection of this information is authorized under 42 USC 285. The primary use of the information you provide is to assess your health and quality of life. The information may be disclosed to clinicians and researchers for research purposes and to monitor personnel to assure that safety standards are maintained. Submission of this information is voluntary.

CUESTIONARIO SOBRE LA CALIDAD DE VIDA – DERMATOLOGÍA

El objetivo de este cuestionario consiste en determinar qué efecto ha tenido su problema de la piel en su vida DURANTE LA ÚLTIMA SEMANA. Por favor marque con una “X” una casilla para cada pregunta.

- | | | | | | |
|----|--|---|--|---------------------|--------------------------|
| 1. | Durante la última semana, ¿ha sentido picazón, dolor o ardor en la piel o la ha tenido adolorida? | Muchísimo
Mucho
Un poco
Nada | 

 | | |
| 2. | Durante la última semana, ¿se ha sentido avergonzado/a o cohibido/a debido a su piel? | Muchísimo
Mucho
Un poco
Nada | 

 | | |
| 3. | Durante la última semana, ¿le ha molestado su condición de la piel para hacer las compras u ocuparse de la casa o el jardín? | Muchísimo
Mucho
Un poco
Nada | 

 | Sin relación |  |
| 4. | Durante la última semana, ¿ha influido su condición de la piel en la elección de la ropa que lleva? | Muchísimo
Mucho
Un poco
Nada | 

 | Sin relación |  |
| 5. | Durante la última semana, ¿ha influido su condición de la piel en alguna actividad social o recreativa? | Muchísimo
Mucho
Un poco
Nada | 

 | Sin relación |  |
| 6. | Durante la última semana, ¿ha tenido dificultad para practicar deportes debido a su condición de la piel? | Muchísimo
Mucho
Un poco
Nada | 

 | Sin relación |  |
| 7. | Durante la última semana, ¿le ha impedido su condición de la piel trabajar o estudiar? | Sí
No | 
 | Sin relación |  |
| | Si la respuesta es "No", durante la última semana, ¿cuánta dificultad le ha ocasionado su condición de la piel en el trabajo o en sus estudios? | Mucho
Un poco
Nada | 

 | | |
| 8. | Durante la última semana, ¿su condición de la piel le ha ocasionado dificultades con su pareja, amigos íntimos o familiares? | Muchísimo
Mucho
Un poco
Nada | 

 | Sin relación |  |
| 9. | Durante la última semana, ¿cuánta dificultad le ha ocasionado su condición de la piel en | Muchísimo
Mucho | 
 | | |

Abbreviated Title: Anakinra in pustular dermatoses

Version Date: December 12, 2018

- su vida sexual? **Un poco** **Sin relación**
- Nada**
-
10. **Durante la última semana, ¿cuánta dificultad le ha ocasionado su tratamiento de la piel, por ejemplo, ocupándole tiempo o ensuciando o desordenando su casa?** **Muchísimo**
- Mucho**
- Un poco**
- Nada** **Sin relación**

Por favor verifique que ha contestado a TODAS las preguntas. Muchas gracias.

La recopilación de esta información está autorizada bajo el Código de los Estados Unidos, número 42 USC 285. La información que usted proporcione será usada principalmente para evaluar su salud y calidad de vida. Esta información podría ser compartida con doctores e investigadores para fines de investigación o con monitores para garantizar que se mantengan las normas de seguridad. El proveer esta información es voluntario.

Abbreviated Title: Anakinra in pustular dermatoses

Version Date: December 12, 2018

19 APPENDIX G: DERMATOLOGY LIFE QUALITY SCORING TOOL

<http://www.dermatology.org.uk/quality/dlqi/quality-dlqi-faqs.html>

The scoring of each answer is as follows:

Very much	scored 3
A lot	scored 2
A little	scored 1
Not at all	scored 0
Not relevant	scored 0
Question unanswered	scored 0
Question 7: "prevented work or studying"	scored 3

The DLQI is calculated by adding the score of each question. The maximum score is 30 and the minimum is 0. The higher the score, the more quality of life is impaired. The DLQI can be expressed as a percentage of the maximum possible score of 30 but we do not recommend this because the "original" score is much easier to understand.

Please Note: The scores associated with the different answers should not be printed on the DLQI itself, as this might cause bias.

Meaning of DLQI Scores

0-1 = no effect at all on patient's life

2-5 = small effect on patient's life

6-10 = moderate effect on patient's life

11-20 = very large effect on patient's life

21-30 = extremely large effect on patient's life

Detailed analysis of the DLQI

The DLQI can also be analyzed under six headings or dimensions as follows:

- Symptoms and feelings Questions 1 and 2 Score maximum 6
- Daily activities Questions 3 and 4 Score maximum 6
- Leisure Questions 5 and 6 Score maximum 6
- Work and School Question 7 Score maximum 3

Abbreviated Title: Anakinra in pustular dermatoses

Version Date: December 12, 2018

- Personal relationships Questions 8 and 9 Score maximum 6
- Treatment Question 10 Score maximum 3

The scores for each of these sections can also be expressed as a percentage of either 6 or 3.

Q. How do you handle missing data from DLQI?

There is a very high success rate of accurate completion of the DLQI. However, sometimes subjects do make mistakes.

- If one question is left unanswered this is scored 0 and the scores are summed and expressed as usual out of a maximum of 30.
- If two or more questions are left unanswered the questionnaire is not scored.
- If question 7 is answered 'yes' this is scored 3 even if in the same question one of the other boxes is ticked.
- If question 7 is answered 'no' or 'not relevant' but then either 'a lot' or 'a little' is ticked this is then scored 2 or 1.
- If two or more response options are ticked for one question, the response option with the highest score should be recorded.
- If there is a response between two tick boxes, the lower of the two score options should be recorded.
- The DLQI can be analyzed by calculating the score for each of its six sub-scales (see above). When using sub-scales, if the answer to one question in a sub-scale is missing, that sub-scale should not be scored.

Collection of this information is authorized under 42 USC 285. The primary use of the information you provide is to assess your health and quality of life. The information may be disclosed to clinicians and researchers for research purposes and to monitor personnel to assure that safety standards are maintained. Submission of this information is voluntary.

Abbreviated Title: Anakinra in pustular dermatoses

Version Date: December 12, 2018

